MEXICAN SOCIAL SECURITY INSTITUTE
EDUCATION, RESEARCH AND HEALTH POLICY UNIT
HEALTH RESEARCH COORDINATION
HIGH SPECIALTY MEDICAL UNIT (UMAE) "DR. BERNARDO SEPÚLVEDA"
CENTRO MÉDICO NACIONAL SIGLO XXI, IMSS, CDMX.
MEDICAL RESEARCH UNIT IN BIOCHEMISTRY.
DEPARTMENT OF NEUROLOGY AND NEUROPHYSIOLOGY.
FAMILY MEDICINE UNITS NUMBER 20, 41 AND 44, IMSS, CDMX.
SPECIALTY OF HUMAN ACUPUNCTURE OF THE ENMH OF THE IPN

Official Title of the study:

“Evaluation of the effect of electroacupuncture on the sensory symptoms of Symmetrical Distal Polyneuropathy of Diabetic origin and its correlation with changes in Nerve Conduction Velocity.”

MEXICAN SOCIAL SECURITY INSTITUTE AND EDUCATION,
RESEARCH AND HEALTH POLICY UNIT STUDY VERIFICATION ID:
R-2020-785-070.
CONBIOÉTICA-09-CEI-009-20160601.

NCT Number: NOT AVAILABLE.

STATISTICAL ANALYSIS
DATE: August 24th, 2022.

A) CALCULATION OF THE SAMPLE SIZE

The calculation of the sample is based on research questions, this is on the effect of electroacupuncture and expected outcomes in relieving sensory symptoms, on changes in sensory and motor VCN and on the patient's quality of life. Therefore, the development of the sample size calculation will be for each outcome variable and in the end the calculations were concentrated in a summary table. We have suggested taking the highest value to be able to have the certainty of having sufficient statistical power and to be able to find all the differences of the proposed average comparisons.

Sample sizes:

1. For the third outcome, related to "relief". Will electroacupuncture be useful in relieving the sensory symptoms produced by PNDs of diabetic origin?

Table 1 of the review of Thakral G et al. (J Diabetes Sci Technol. 2013, 1;7(5):1202-9) was used as a reference, where different reports of the response and usefulness of electrical stimulation as a complementary treatment of painful and sensory diabetic neuropathy were analyzed and compared, according to this analysis the work of Dinesh Kumar et al. (Diabetes Care 1998, 21 (8): 1322-1325). Where we take into account the reported decrease in neuropathic symptoms with the use of electrical stimulation ($66 \pm 10\%$) when compared to a Sham ($55 \pm 12\%$). For the calculation of the N we use the comparison of means. ^{73,74}

	$n = K [(s_1)^2 + (s_2)^2] / (M_1 - M_2)^2$
K	14.884164 (Za+Zb) ²
s1	10 Standard deviation of group 1
s2	12 Standard deviation of group 2
m1	66 Group 1 Average
m2	55 Group 2 Average
n per group=	30
n total=	60
Za	2.576
Zb	1.282

For this research question a total of 60 subjects will be required, 30 for each group under study.

2. For the second outcome, will the use of electroacupuncture generate changes in the study of sensory and motor NCV by electrophysiological techniques?

For the question, it is calculated considering the mean and SD resulting at the beginning and end of the intervention of the changes of the NCV of Yanqing Tong et al. of 48.2 ± 0.6 vs 46.2 ± 0.7 (m / s).⁶¹ A comparison of means was made, with the test assumption of a bilateral hypothesis, with a Confidence or Security Level (1- α): 95%, Statistical Power of 80%, Accuracy (d) of 20%, the resulting sample size was:

196 subjects per group

3. For the third outcome, will the use of electroacupuncture generate improvement in the evaluation of the patient's quality of life as measured by the SF36?

So far there is no publication that analyzes the perception of an improvement in quality of life in subjects with diabetic neuropathy with the use of electroacupuncture. Therefore, we have raised the size according to those described in the article by *Kongkiat Kulkantrakorn et al.*⁷⁵ where the aforementioned authors made a "baseline" estimate of the perception of the quality of life of the patient with diabetic foot in 8 domains of the SF-36. Our proposal is that there will be an improvement in the quality of life, in all the domains described, that is, it will be at least equal or better, we have taken into account the average of the physical function which is the deteriorated of 18.9.

Table 4: Comparison of SF-36 mean score in relevant studies

Domains	Multiple sclerosis* (N=85)	Epilepsy* (N=271)	Diabetes* (N=555)	Diabetic foot ulcer [†] (Thailand) (N=40)	Healthy Thai adults [‡] (N=1,345)	PDN current study (N=33) [§]	Current study [§] VS Healthy Thai adults [‡] (P value)
Physical function	33.5	78.9	74.2	18.9	77.3±17.4	31.5±27.7	<0.001 [†]
Role limitation due to physical problem	32.7	60.0	55.1	27.5	82.2±28.6	40.2±39.0	<0.001 [†]
Bodily pain	72.2	72.8	71.7	32.5	75.6±18.4	47.3±30.6	<0.001 [†]
General health	53.7	68.7	52.6	79.5	65.1±18.1	50.8±28.5	0.007 [†]
Vitality	41.9	55.4	54.3	70.9	62.2±13.3	60.9±35.9	0.63
Social functioning	60.2	77.3	81.2	50.9	78.2±18.2	63.6±29.7	0.008 [†]
Role limitation due to emotional problem	59.6	66.3	70.2	51.6	80.4±31.9	42.4±43.5	<0.001 [†]
Emotional well being	67.8	68.4	73.0	36.6	66.1±12.9	39.4±30.7	<0.001 [†]

*Reference 22; [†]Reference 20; [‡]Reference 8; [§]Current study; [†]Statistically significant; PDN: Painful diabetic neuropathy; SF-36: Short form 36 quality of life questionnaires

Table taken from J Neurosci Rural Pract. 2013 Jul-Sep; 4(3): 267–270.⁷⁵

Making a comparison of averages:

$$n = K [(s1)^2 + (s2)^2] / (M1 - M2)^2$$

K	14.884164	(Za+Zb) ²
s1	7.37	Standard deviation of group 1
s2	27.7	Standard deviation of group 2
m1	31.5	Group 1 Average
m2	18.9	Group 2 Average
n per group=	77	
n total=	154	
Za	2.576	
Zb	1.282	

NOTE: As we discussed previously, we have suggested taking the highest value in order to be sure of having sufficient statistical power and to find all the differences in the proposed mean comparisons of each outcome (that is, the effect of Electroacupuncture compared to sham on the following outcome variables).

Each group was added 20% of the N for possible losses.

OUTCOME VARIABLE	N PER GROUP	ALPHA Z	Z DE BETA	PLUS 20% OF POSSIBLE LOSSES PER GROUP	STUDY TOTAL
Relief of sensory symptoms	30	2.576	1.282	36 Total :36	72
Changes in the study of sensory and motor VCN	109	2.576	1.282	130.8 Total: 131	262
Improvement in quality of life assessment	77	2.576	1.282	92.4 Total: 93	186

The sample of the present study was estimated at 109 for each group, however, 20% was added considering possible losses (each group will be 131), therefore, the total N of the study is 262.

It is important to mention that the way to obtain the sample will be by number of consecutive cases of candidate patients who go to the outpatient consultation of the UMF 20, 41 and 44 of the IMSS of the CDMX, for their subsequent evaluation in the screening and respective randomization in case of being included in the study.

VARIABLES

TABLE 1. CATEGORIZATION OF VARIABLES

	VARIABLE	MEASURING INSTRUMENT	TYPE AND SCALE OF MEASUREMENT	UNITS
DEPENDENT	Sensitive commitment	MDNS	Ordinal qualitative	Normal, diminished and absent
	Brawn	MDNS	Ordinal qualitative	Normal, moderate, severe and absent
	Reflexes	MDNS	Ordinal qualitative	Present, present with effort and absent.
	Sensory symptoms	MNSI	Discrete Quantitative	Dichotomous Response (Yes, No) Evaluation score 13 out of 15
	Aquilian reflex	MNSI	Ordinal qualitative	Present, present with effort and absent.
	Vibration perception	MNSI	Ordinal qualitative	Present, present with effort and absent.
	Pain scale	NRS	Discrete Quantitative	Evaluation score 0-10
	Physical function	SF 36	Ordinal qualitative	Excellent, very good, good, regular, bad
	Physical role	SF 36	Ordinal qualitative	Yes, it limits me a lot /Yes, it limits me a little/ No, it doesn't limit me at all.
	Body pain	SF 36	Ordinal qualitative	No, none/ Yes, very little/ Yes, a little/ Yes moderate/ Yes, a lot/ Yes, a lot
	General health	SF 36	Ordinal qualitative	Nothing, a little, Regular, quite, a lot.
	Vitality	SF 36	Ordinal qualitative	Always, almost always, sometimes, only once, never.
	Social function	SF 36	Ordinal qualitative	Always, almost always, sometimes, only once, never.
	Emotional role	SF 36	Ordinal qualitative	Always, almost always, sometimes, only once, never
	Mental health	SF 36	Ordinal qualitative	Totally true, Quite true, I don't know, Quite false, Totally false
	VCN	Electrophysiological techniques (Nicolet, Viking Model IV D, 4 channels)	Continuous quantitative	Latency (ms) Amplitude (mV) Distance (mm) Speed (m/s)
INDEPENDENT	Electroacupuntal points	Zusanli (E36)	Dichotomous qualitative	Dichotomous (Yes, No)
		Fenlong (E40)	Dichotomous qualitative	Dichotomous (Yes, No)
		Yinlingquan(B9)	Dichotomous qualitative	Dichotomous (Yes, No)
		Sanyinjiao (B6)	Dichotomous	Dichotomous

			qualitative	(Yes, No)
		Taichong (H3)	Dichotomous qualitative	Dichotomous (Yes, No)
		Zulinqi (VB41)	Dichotomous qualitative	Dichotomous (Yes, No)
CONFUSING	Age	Years	Discrete quantitative	40-70 years
	Fasting glyceimic control	mg/dl	Discrete Quantitative	100 -180 mg/dl
	Glycosylated hemoglobin concentration	Percentage	Continuous Quantitative	7-10 %
	DM evolution time	Years	Discrete quantitative	5-15 years of evolution
	BMI	Kg/m ²	Discrete quantitative	18-40 Kg/m ²
	Pressure	Mmhg	Discrete quantitative	90/60 mmHg-200/160 mmHg

STATISTICAL ANALYSIS

The collected variables will be integrated into a database in Excel and then analyzed in SPSS (Statistical Product and Service Solutions) for Windows in the 2019 version. The descriptive analysis of the information collected will be carried out using simple and absolute frequencies, as well as measures of central tendency and dispersion. Once the variables have been collected, the Shapiro-Wilk statistic will be applied to determine if their distribution is normal or not.

The statistical methods to be used will be two-tailed t-tests for comparison of mean value between groups, paired t-tests will be used for comparison of mean values within groups, and repeated two-way analysis of variance for changes in NCV, pain threshold and glucose concentrations.

To evaluate the degree of association between variables and covariates, univariate and bivariate models will be used using the X² test or Fisher's exact test for discrete variables; or the Student's t test, for continuous variables.

The analysis of these tests will be carried out by means of the Mann-Whitney U statistical test, or by means of ANOVA-type statistical measurement. Correlation studies will be performed by Pearson or Spearman Test.

A multivariate analysis will be carried out including the confounding variables (age, time of evolution of DM, anthropometric and biochemical parameters) using a non-conditional logistic regression model, for discrete dependent variables; and a linear regression model for continuous dependent variables.

The analysis of clinical improvement by means of the MDNS scale, the MNSI and the SF-36 will be performed by means of the Mann-Whitney U statistical test. The analysis of nerve conduction velocities shall be carried out by means of ANOVA-type statistical measurement.

It is contemplated to perform an analysis of multiple results and by subgroups, that is, by stratification according to age, time of diagnosis of DM, degree of affection, scale of pain and type of conventional pharmacological treatment, evaluating sensation and perception of the stimulus of pain, vibration, reflexes, VCN by electrophysiological techniques.

Although both groups may have improvement due to conventional treatment, significant differences or trends in the electroacupuncture group are expected, the analysis will include logistic regression analyzing the confounding variables.

For all tests a value of $p < 0.05$ shall be considered statistically significant.

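### The NCV outcome sets N = 262, but its assumed effect is described as a start-to-end change, so the power stated for electroacupuncture versus sham on NCV is unsupported

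*SAP*

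**What the plan says.** All references are to the SAP.

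- **Section A, item 2 (NCV).** The effect comes from one cited study, 48.2 ± 0.6 vs 46.2 ± 0.7 m/s, introduced with the words "it is calculated considering the mean and SD resulting at the beginning and end of the intervention of the changes of the NCV". The figures enter a comparison of means "with the test assumption of a bilateral hypothesis", at 95% confidence, 80% power and an accuracy (d) of 20%. The result is given as "196 subjects per group".
- **Section A, NOTE and summary table.** The NOTE defines the comparisons to be powered as "the effect of Electroacupuncture compared to sham on the following outcome variables". The NCV row shows 109 per group with z-values 2.576 and 1.282. It is the largest row and fixes the trial: "The sample of the present study was estimated at 109 for each group", raised to 131 per group and 262 in total.
- **Section A, item 1 (relief).** Here the effect is a between-arm one: 66 ± 10% on electrical stimulation "when compared to a Sham" (55 ± 12%).
- **Statistical Analysis.** Improvement from usual therapy is anticipated in either arm. Between-group t-tests, within-group paired t-tests and a two-way repeated-measures ANOVA for NCV are planned. Significance is p < 0.05 throughout.

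No NCV change under sham appears anywhere in the SAP.

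**The concern.** A start-to-end change within a treated group contains everything that happens over the treatment period: the specific effect, the response to a sham procedure, background therapy and drift. The electroacupuncture-minus-sham difference keeps only the part that differs between arms. The two coincide only if NCV under sham does not change, and the SAP does not assume that.

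This matters most for NCV because that row sets N. Relief is planned on an active-versus-sham difference and NCV on a start-to-end one, yet both sit in one table under one claim of adequate power. As written, no assumed electroacupuncture-minus-sham difference lies behind the row that determines the size of the trial, and a null NCV result would have no planned between-arm effect to be read against.

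**Working it through.** **Inputs.** From item 2: means 48.2 and 46.2 (difference 2.0 m/s), SDs 0.6 and 0.7. The sum of squared SDs is 0.36 + 0.49 = 0.85, and the root-mean-square SD is √(0.85/2) = 0.652. From the summary table: Za = 2.576 and Zb = 1.282, so K = 3.858² = 14.884 (two-sided 1%, 90% power). For item 2's 95%/80%, K = 7.849. For 5%/90%, K = 10.507.

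**Step 1: does the SAP's formula work elsewhere?** n = K(s1² + s2²)/(M1 − M2)².
- Item 1: 14.884 × (100 + 144)/11² = 30.0; stated 30.
- Item 3: 14.884 × (7.37² + 27.7²)/12.6² = 77.0; stated 77.

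Both are reproduced.

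**Step 2: the same formula on the NCV figures.**
- 95%/80%: 7.849 × 0.85/4 = 1.67, i.e. 2 per group.
- 99%/90%: 14.884 × 0.85/4 = 3.16, i.e. 4 per group.

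Neither 196 nor 109 results. Of the variants tried, only 7.849/0.2² = 196.2 matches 196. That is a one-sample or paired formula with a standardized effect of 0.2; the two-sample version is 2 × 7.849/0.2² = 392.4, i.e. 393 per arm. Reading the 20% accuracy as a standardized effect of 0.2 is an inference. No variant tried gives 109. With a 2.0 m/s difference, 109 per arm would need a common SD of about 5.3 (95%/80%) or 3.8 (99%/90%), against the stated 0.6 to 0.7.

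**Step 3: how much the missing sham change matters.** The SAP gives no figure, so assume that sham achieves a fraction f of the 2.0 m/s. The between-arm difference is then 2.0 × (1 − f). Power is for 109 per arm, two-sided 5%:

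| f | Difference (m/s) | SD assumed | n per arm, 5%/80% | Power with 109 |
|---|---|---|---|---|
| 0 | 2.0 | 0.652 | 2 | >99.9% |
| 0.5 | 1.0 | 0.652 | 7 | >99.9% |
| 0.75 | 0.5 | 0.652 | 27 | >99.9% |
| 0.85 | 0.3 | 0.652 | 75 | 92% |
| 0.9 | 0.2 | 0.652 | 167 | 62% |
| 0.95 | 0.1 | 0.652 | 668 | 20% |
| 0 | 2.0 | 5 (assumption) | 99 | 84% |
| 0.5 | 1.0 | 5 (assumption) | 393 | 31% |

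The answer runs from ample to poor power depending on two quantities the SAP does not supply: the sham change, and the SD of the NCV measure as it will be analysed.

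**Step 4: what the planned N can detect between arms.** 131 per arm less 20% leaves 131 × 0.8 = 104.8, about 105 evaluable (the SAP multiplied 109 by 1.2, so the 20% loss takes it slightly below 109). Detectable standardized difference = √(2K/n):
- 5%/90%: √(2 × 10.507/105) = 0.45 SD
- 5%/80%: √(2 × 7.849/105) = 0.39 SD
- 1%/90%: √(2 × 14.884/105) = 0.53 SD

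In m/s at 5%/90%, 0.447 SD is 0.447 × 0.652 = 0.29 if the SD is 0.652, or 0.447 × 5 = 2.2 if it is 5.

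**The case against.** The strongest reply is that the sentence in item 2 is garbled and may not mean what it says. Taken in order, 48.2 at the beginning and 46.2 at the end is a fall in conduction velocity, an odd effect to plan for a treatment expected to help. Item 1 lists the active group first, and item 2 speaks of a comparison of means and of subjects per group, so the figures could be two arms. Only the cited study can settle this. The reply stands as far as it goes, but it does not clear the plan: if the figures are a between-arm contrast, the SAP describes them wrongly.

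A second reply is that, since neither 196 nor 109 follows from these figures, N has not been shown to rest numerically on the start-to-end change. That is correct. What can be said is that the start-to-end change is the only NCV effect the SAP offers in support of N. The conflicting sizes and error rates also mean that no single stated power attaches to 109.

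Two stronger readings should be resisted. A reader might infer that the trial never tests the start-to-end contrast; the Statistical Analysis section plans paired within-group tests, so it may well do so. The exact point is that this is not the contrast the NOTE says N powers. A reader might also infer that the trial is underpowered for NCV. With the quoted SDs it is not, unless sham achieves more than roughly 85% of the change. Even if the sham share of relief in item 1 (55/66, a between-arm remainder of 11/66, or 0.33 m/s) carried over to NCV, 109 per arm would have about 97% power at 5% and 88% at 1%.

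**Conclusion.** The mismatch is in the text. The outcome that sets N = 262 is justified by an effect described as start-to-end, while N is declared to power electroacupuncture against sham. With no sham NCV change given and improvement anticipated in both arms, the power claimed for that contrast is unsupported. The direction and size of the error cannot be determined: with 109 per arm at 5%, power runs from over 99.9% (quoted SDs, sham change up to 75% of the total) to 31% (assumed SD 5 m/s, sham change half of the total). These scenarios are assumptions.

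The internal conflicts in the same calculation are certain: 196 versus 109 per group, 95%/80% versus 99%/90%, and an n that its own inputs do not produce. The 1% level in the table also disagrees with the p < 0.05 rule. Reconciling these alone would not cure the point, because a tidy n built on a start-to-end change would still plan the wrong quantity.

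**What to change.** Keep N = 262 and rewrite item 2 and the NCV row of the summary table:

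1. Remove the beginning/end figures as the assumed between-arm effect. If the cited study shows that they are an active-versus-sham contrast, correct the description instead and say which figure belongs to which arm.
2. State one n in place of 196 and 109, and one alpha/power pair. The p < 0.05 rule points to two-sided 5%; the sponsor should choose 80% or 90% power and use it in both text and table.
3. State the row as a detectable difference, for example: with 131 randomized per arm and 20% loss (about 105 evaluable), the trial has 90% power at two-sided 5% for an electroacupuncture-minus-sham difference of about 0.45 SD of the analysed NCV measure (0.39 SD at 80% power).
4. If an active-versus-sham NCV change and its SD are available, give the difference in m/s beside it, with a sentence on whether a difference of that size matters.

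The cost is SAP wording only: no added patients, visits or measurements. The relief and quality-of-life rows use the same z-values, so they should be restated if the pair changes. A 5% level with 80% or 90% power only lowers their n, so N is not affected.

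### The nerve conduction velocity outcome sets the trial's size, but the SAP gives two conflicting sizes for it (196 and 109 per group), and neither follows from its stated inputs

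*SAP*

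**What the plan says.** All of this is in the SAP, section A, Calculation of the sample size.

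- **Introduction.** Each outcome is sized separately, and "in the end the calculations were concentrated in a summary table". The highest value is to be used.
- **Item 2 (NCV).** The inputs are 48.2 ± 0.6 and 46.2 ± 0.7 m/s from a cited study, described as the "mean and SD resulting at the beginning and end of the intervention". The test is two-sided at 95% confidence. The item ends with "Statistical Power of 80%, Accuracy (d) of 20%, the resulting sample size was" and then "196 subjects per group".
- **NOTE before the summary table.** It repeats the rule: "we have suggested taking the highest value in order to be sure of having sufficient statistical power". It describes the comparisons as "the effect of Electroacupuncture compared to sham on the following outcome variables".
- **Summary table.** NCV has 109 per group, with Z values of 2.576 and 1.282. For losses, "Each group was added 20% of the N for possible losses", giving 130.8, rounded to 131 per group and 262 in total. The other rows are 30 per group (relief) and 77 per group (quality of life).
- **Conclusion.** "The sample of the present study was estimated at 109 for each group", and the study total is 262.

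The Statistical Analysis section closes by setting significance at p < 0.05 for all tests.

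**The concern.** NCV is the row that fixes the size of the whole trial: without it, quality of life would govern at 186 in total. Yet the SAP sizes NCV twice, with different alpha, power and results. Because alpha and power change along with the number, a simple slip between 196 and 109 does not explain the difference. The larger figure is dropped without comment, in a plan that says the largest is taken, and no calculation is shown for the smaller one.

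What is at stake is the justification for 262 patients. If the basis for N is unknown, nobody can judge whether the trial is too small, too large or adequate for NCV, or what a null NCV result would mean.

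**Working it through.** **Formula.** The SAP prints n per group = K(s1² + s2²)/(M1 − M2)², with K = (Zα + Zβ)². At the table's Z values, K = (2.576 + 1.282)² = 14.884. At two-sided 5% and 80% power, K = 7.849.

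**The formula reproduces the other two rows.**
- Relief: 14.884 × (10² + 12²)/11² = 14.884 × 244/121 = 30.0 (SAP: 30).
- Quality of life: 14.884 × (7.37² + 27.7²)/12.6² = 77.0 (SAP: 77).

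**The same formula for NCV.** s1² + s2² = 0.36 + 0.49 = 0.85, and the difference is 48.2 − 46.2 = 2.0 m/s.
- Table's Z values: 14.884 × 0.85/4 = 3.16, so 4 per group.
- Item 2's 5% and 80%: 7.849 × 0.85/4 = 1.67, so 2 per group.

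**Inputs that would give 109.**
- At 1%/90%: a difference of √(14.884 × 0.85/109) = 0.34 m/s with the printed SDs, or an SD of √(109 × 4/(2 × 14.884)) = 3.83 m/s with the printed difference.
- At 5%/80%: 0.247 m/s, or an SD of 5.27 m/s.

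None of these values is in the SAP.

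**Possible readings of the 20% accuracy term d**, which has no unit or definition:

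| Reading of d | Alpha/power | n |
|---|---|---|
| 0.2 SD, one-sample form: 7.849/0.04 | 5%/80% | 196.2 |
| 0.2 m/s, SD 0.7 in both groups: 7.849 × 0.98/0.04 | 5%/80% | 192.3 per group (193.3 t-based) |
| 0.2 m/s, printed SDs: 7.849 × 0.85/0.04 | 5%/80% | 166.8, so 167 per group |
| 20% of 2.0 = 0.4 m/s, printed SDs: 7.849 × 0.85/0.16 | 5%/80% | 41.7, so 42 per group |
| 0.4 m/s, printed SDs: 14.884 × 0.85/0.16 | 1%/90% | 79.1, so 80 per group |

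So 196 is reached, or nearly reached, only by setting aside the 2.0 m/s difference. None of these readings gives 109. The nearest miss found with a simple reading is 112 (one-sided 5%, 80% power, 0.2 m/s, SD 0.6), which contradicts both the two-sided test in item 2 and the table's Z values.

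**Power, two-sample t-test.**
- Printed difference of 2.0 m/s, pooled SD √(0.85/2) = 0.652, 109 per group: about 100%.
- Assumed 0.2 m/s with SD 0.7 (not stated in the SAP; it is the two-group reading that comes near 196): at two-sided 5%, 81% with 196 per group and 56% with 109; at two-sided 1%, 31% with 109.

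**What 131 per group can detect.** If 20% of those enrolled are lost, 131 × 0.8 = 104.8, about 105 per group. The t-based detectable differences are below; the last column multiplies by an SD of 0.6 to 0.7 m/s.

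| Alpha/power | In SD units | In m/s |
|---|---|---|
| 5%/80% | 0.39 | 0.23–0.27 |
| 5%/90% | 0.45 | 0.27–0.31 |
| 1%/90% | 0.54 | 0.32–0.38 |

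**If 196 governs**, with the SAP's own allowance: 196 × 1.2 = 235.2, so 236 per group; 2 × 236 = 472; 472 − 262 = 210 more.

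**The case against.** The strongest reply is that the operative size is not in doubt. The introduction sends the reader to the table, 109 is the largest entry in it, the conclusion repeats 109, and 109 × 1.2 = 130.8 leads correctly to 131 and 262. That stands: within the table the highest-value rule is obeyed. But it settles only which number is used, not where it comes from, and 196 remains in the current text for the same outcome.

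A second reply is that no loss of power has been shown. This also stands. For the only printed NCV difference, 109 per group is far more than enough, and it exceeds the 30 and 77 required for the other outcomes.

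Third, the figures of 81%, 56% and 31% rest on an assumed 0.2 m/s with SD 0.7 in both groups, whereas the printed SDs are 0.6 and 0.7. Likewise, the exact match for 196 is a one-sample or paired size, which is not a between-arm requirement, so 472 is not an established need. Both points are fair. These figures show how far the answer moves with the reading; they do not measure a known shortfall.

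Finally, 105 evaluable assumes that 20% of those enrolled are lost. Under the SAP's additive convention 131 corresponds to 109 evaluable, and the 5%/80% detectable difference becomes 0.38 SD instead of 0.39. The change is negligible.

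**Conclusion.** The concern holds and must be fixed. The SAP gives 196 per group (5%/80%) and 109 per group (1%/90%) for the outcome that sets N, and does not reconcile them. Neither follows from the printed means and SDs, which give 2 and 4 per group respectively. That conclusion needs no assumption beyond the SAP's own formula, which its other two rows confirm.

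The direction of the error is open. If 2.0 m/s is the target, NCV needs only 4 per group, quality of life would set the total at 186, and 262 − 186 = 76 patients have no stated reason. If 196 is a genuine between-arm requirement, the plan falls 210 short. Restoring 196 alone would not be a justified repair.

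A secondary and less certain point is that item 2 can be read as a before-and-after contrast, while the NOTE describes a comparison with sham. The text does not settle which kind of difference 48.2 versus 46.2 represents.

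**What to change.** 1. State one alpha and power pair for the NCV row, and one between-arm NCV difference with its SD in m/s. A 5% alpha would agree with item 2 and with the p < 0.05 rule in the Statistical Analysis section; if the table's 1% is kept, explain how it fits with that rule.
2. Define the 20% accuracy term or remove it.
3. Delete whichever of 196 and 109 is superseded, and make the highest-value statement match what was done.
4. If 131 per group is kept, replace the NCV justification with what that size delivers. For example: 131 per group, about 105 evaluable if 20% of those enrolled are lost, detects a between-arm difference of 0.39 SD with 80% power (0.45 SD with 90%) at two-sided 5%, with assumed SD = [value] m/s. If 1%/90% is kept, the figure is 0.54 SD.
5. If the sponsor holds that 196 per group is required, say plainly that 262 does not meet it (236 per group and 472 in total by the SAP's own allowance).

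**Cost.** If 262 stands, this is SAP wording and one table row, with no extra patients. The stated detectable difference may look less favourable if the true SD exceeds 0.6–0.7 m/s. If 196 is required, the choice is 210 more patients or an explicit statement that the NCV requirement is not met.

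### The SF-36 row (77 per group) rests on a gap between two disease samples and an SD that cannot be traced; with the tabulated SD in both arms, 109 is not the highest requirement at the row's own 1% level, and at 5% there is no real margin

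*SAP*

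**What the plan says.** The SAP sizes each outcome separately in section A, Calculation of the sample size, and takes the largest result. For SF-36 (item 3) it states that no publication on electroacupuncture and quality of life exists in this disease, and turns to a published baseline description: "we have taken into account the average of the physical function which is the deteriorated of 18.9". The calculation box enters means 31.5 and 18.9, SDs 7.37 and 27.7, Z-alpha 2.576 and Z-beta 1.282 into "n = K [(s1)^2 + (s2)^2] / (M1 - M2)^2" and reports 77 per group.

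In the reproduced Table 4, the physical-function entry 31.5±27.7 belongs to the painful diabetic neuropathy sample (N=33). The entry 18.9, with no SD, belongs to the diabetic foot ulcer sample (N=40), which is footnoted to a different reference.

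The NOTE after the box says the rows concern electroacupuncture compared with sham, and that taking the highest value gives enough power "to find all the differences in the proposed mean comparisons of each outcome". The closing paragraph reads "The sample of the present study was estimated at 109 for each group", raised to 131 for losses. The Statistical Analysis section assigns SF-36 to the Mann-Whitney U test and says that p<0.05 "shall be considered statistically significant" for all tests.

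**The concern.** Two inputs to the row do not represent what the row is used for.

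- **The difference.** A gap between patients with painful neuropathy and patients with foot ulcers says nothing about how far treated and sham patients will differ. Lack of published data is a fair reason to assume a value. The SAP gives no reason for assuming this one.
- **The SD.** The box pairs the mean 31.5 with 7.37, while the table prints 27.7 beside that mean. The value 7.37 appears only in the box. If it is too small, the row understates the number needed.

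At stake is the statement that the highest of the three rows assures power for every outcome. That statement is only as good as each row, and this row is also computed at a stricter alpha than the analysis uses.

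**Working it through.** **Inputs.** From the box: K = (2.576 + 1.282)² = 14.884164, which is two-sided 1% and 90% power; difference 31.5 − 18.9 = 12.6; SDs 7.37 and 27.7. From the analysis section: alpha 0.05, Mann-Whitney for SF-36. From the closing paragraph: 109 per group, 131 enrolled.

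**1. The plan's own figure.** 14.884164 × (7.37² + 27.7²) / 12.6² = 77.03, against 77 stated. The arithmetic is sound. Swapping the two SDs between groups leaves n unchanged, so the pairing itself does not move the result; the size of 7.37 does.

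**2. Illustration: 27.7 in both arms, 12.6 kept, 90% power.** The assumption is mine: 27.7 is the only neuropathy SD the table gives for this domain.

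- At the row's 1% level: 14.884164 × 2 × 27.7² / 12.6² = 143.87, so 144 per group.
- At 5%: K = (1.96 + 1.282)² = 10.5106, and 10.5106 × 2 × 27.7² / 12.6² = 101.60, so 102 per group.

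**3. Power for a difference in means.** Power = Φ(12.6 / (27.7 × √(2/n)) − z), with z = 1.96 or 2.576. The planned 131 less 20% is 131 × 0.8 = 104.8, about 105.

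| n per group | 5% | 1% |
|---|---|---|
| 77 (the row) | 81% | 60% |
| 105 (131 less 20%) | 91% | 76% |
| 109 | 92% | 78% |

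**4. The planned test.** Assume a Mann-Whitney efficiency of 0.955 relative to the t-test, the value for a normal shift. Then 101.60 / 0.955 = 106.4, so 107 per group at 5%. With 105 per group the effective size is 105 × 0.955 = 100.3, and power is Φ(0.4549 × √(100.3/2) − 1.96) = Φ(1.26), about 90% (89.6%). A skewed score could move this either way.

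**5. Sensitivity to the unexplained difference.** At 10 points instead of 12.6, still with SD 27.7, 5% and 90% power: 10.5106 × 2 × 27.7² / 10² = 161.3, so 162 per group.

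**The case against.** The strongest reply is that nothing in the trial turns on this row. The NCV row sets the size, the SF-36 arithmetic reproduces, and at the 5% level of the analysis the planned numbers give about 90% power even with the larger SD. The adverse figures (144 per group, 76-78% power) need both the substituted SD and the 1% level, which the analysis section does not use. This stands, and it is why the point is minor. It does not rescue the row: its inputs remain unsupported, and 1% is the level that the box and summary table themselves list.

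It can also be said that 27.7 is one choice among several. It comes from 33 patients, and adjusting for the baseline score would lower the effective SD. That too is fair, so 102, 107 and 144 are illustrations. The SAP's listed adjustment variables do not include the baseline score, however, and the planned SF-36 comparison is unadjusted.

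Three stronger readings are tempting, and the document does not support them:

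- A reader might infer that 7.37 is an error. The cited articles are not reproduced beyond one table, so all that can be said is that it cannot be traced here.
- A reader might compare the two columns across all eight domains and conclude that the improvement the SAP expects is contradicted. The SAP sizes on physical function only, and it qualifies its expectation as scores at least equal or better.
- A reader might infer that the planned size safely covers SF-36 at 5%. About 105 evaluable exceeds 102 but not 107, and both figures depend on a 12.6-point difference with no stated basis.

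**Conclusion.** Minor, but wrong as written. The row presents a difference between two descriptive disease samples as an electroacupuncture-versus-sham effect, and uses an SD that the document does not source.

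With 27.7 in both arms and 12.6 points kept, the statement that 109 is the highest requirement fails at the row's own Z values: 144 are needed, and 109 give about 78% power instead of 90%. At the analysis level of 5%, about 105 evaluable per group give roughly 90-91% power, with no real margin.

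These figures rest on normal theory, a common SD of 27.7, an assumed Mann-Whitney efficiency of 0.955 where stated, and 12.6 taken at face value. They do not show the trial to be underpowered. They show that the assurance of power for this outcome is not supported by the inputs given. The separate inconsistency between 196 and 109 for NCV is not relied on here.

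**What to change.** In item 3 and the summary table:

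1. Give the source of 7.37, or replace it with 27.7 in both arms and label that an assumption.
2. State 12.6 points as an assumed electroacupuncture-minus-sham difference, with a reason, and do not present it as derived from Table 4.
3. Restate the row at the alpha used in the analysis and for the planned test. Under 27.7, two-sided 5% and 90% power, this is 102 per group for means, or about 107 for Mann-Whitney at the stated efficiency.
4. Report power at the planned size after losses: about 90-91% at 5%. If the 1% level is kept, about 76% by normal theory for means.
5. Qualify the statement that the highest value assures power for every outcome.

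The cost is one restated row and a few sentences. No change in enrolment is proposed.
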